Hypertension is a common but frequently overlooked and underreported adverse effect of erythropoietin (EPO) therapy ¹⁻⁶. Although EPO was approved in 1989 for treatment of anemia in patients with chronic kidney disease (CKD), only recently have trials noted substantial cardiovascular risks associated with normalization of hemoglobin ⁷⁻¹⁰. In the largest of these randomized trials, Trial to Reduce Cardiovascular Events with Aranesp Therapy (TREAT), the risk of stroke was increased twofold with EPO therapy ¹⁰. Stroke risk is strongly related to poorly controlled hypertension. Blood pressure was not measured the way it usually is in hypertension trials, so we cannot be completely confident that the increased stroke risk in this large, randomized trial was not related to EPO-induced hypertension (EIH). Furthermore, new therapies, such as hypoxia-inducible factor (HIF) stabilizers, are on the horizon. It remains to be seen whether these new drugs would have a lower or a higher risk for hypertension compared to EPO. Accordingly, understanding the mechanism of EPO-induced hypertension is urgent ¹¹. Animal and human experiments suggest that endothelial dysfunction is central to the genesis of EPO-induced hypertension (EIH).

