Harms will be assessed by monitoring changes in weight, eGFR, CBC, clinic BP, and ABPM. For more definitive assessments, including hospitalizations, serious adverse events will be properly completed and sent to the VAMC DMC as requested. Safety of continued participation will be assessed at each study visit. The stop-points will be treatment-emergent severe adverse events that precludes further exposure to the drug, such as an allergic drug reaction, initiation of renal replacement therapy, or death. If the study drug is stopped, the subject will be continued to be studied so as to not violate the intention-to-treat principle.

Participants

Inclusion Criteria

- Stage 3 or 4 CKD defined as eGFR <60mL/min/1.73m² for ≥3 months or persistent albuminuria for ≥3 months; (i) urine albumin to creatinine ratio of more than 30 mg/g; (ii) urine protein to creatinine ratio of more than 150 mg/g; or (iii) at least 1+ dipstick positive proteinuria. ⁸⁸
- 24h ABPM <140/90 mmHg at baseline in the presence or absence of antihypertensive treatment.
- Hgb between 8 and 10 g/dL.
- No treatment with ESA within the previous 3 months.
- Adults, age 18 and older.

Exclusion Criteria

- Need for packed RBC transfusion in the previous 2 months.
- Myocardial infarction, stroke, or hospitalization for heart failure in the past 2 months.
- In the assessment of the investigator, have hematologic, inflammatory, infectious, or other conditions that might interfere with the erythropoietic response.

Retention of Participants

For half of the participants, only 7 visits are needed. For the others, at least 11 visits over 24 weeks of the trial are needed. We will offer \$20 per visit for participation in the trial to offset travel and time costs.

METHODS

Method of Randomization

Participants will be randomized in a 1:1 ratio to either early or delayed treatment (“waitlisted group”) with EPO according to UACR strata. A random permuted block design will be used to avoid imbalance in assignment to the treatment groups over time. A randomization sequence will be generated by the statistician and individually concealed in sequentially numbered opaque envelopes. After confirming eligibility with the principal investigator, the study pharmacist will dispense EPO according to the randomization sequence.

Measurement of clinic BP

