2. Change from baseline to 12 weeks in systolic BP in the comparisons above. Between group change in hypertension status from baseline to 12 weeks. Worsening of hypertension at any time point will be defined either as an increase in BP medication or an increase in seated clinic diastolic BP of ≥ 10 mmHg or systolic BP ≥ 20 mmHg. Within-group change in hypertension status from 12w to 24 w will be compared to the control period of 0 to 12w in the delayed start group.
3. The primary outcome variable in this aim is to examine the change in FMD from baseline to 4 weeks in those treated with EPO compared to the waitlisted group. The hypothesis being tested is that EPO will cause impairment in endothelial function. Accordingly, those on EPO will have worsening of FMD.
4. The primary outcome variable in this aim is to examine the predictors of change in FMD from baseline to 4 w in those treated with EPO compared to time controls. Predictors of this change will be baseline values of the following variables: ADMA, urine nitrate and nitrite, renin, aldosterone, and plasma endothelin-1 and change from baseline to 4 w in the above variables. This analysis will answer the question: which of the pathways independently is predictive of endothelial dysfunction?

Sample Size

The primary objective of the study is to assess the change from baseline to 12 weeks in diastolic BP in EPO treated patients compared to controls. In the waitlisted group, we will measure the change from 12 weeks to 24 weeks compared to the change from 0 to 12 weeks. We have measured 24h

ambulatory BP in 183 CKD patients 4 weeks apart. The mean diastolic BP at baseline was 68.3 mmHg and at 4 weeks 68.1 mmHg. The mean difference was 0.14 mmHg and the standard deviation of the difference was 10.3 mmHg. With these assumptions, two-tailed tests and 80% power, the required sample size to detect a between-group difference of 5 mmHg is 68 subjects completing the study in each group. Assuming 85% of those randomized complete the trial, we would need to randomize $68/0.85 = 80$ subjects per group, or 160 subjects in total.

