The number of subjects who experience hypokalemia, hypercalcemia, gout, hospitalization for diabetes mellitus, transient elevations in serum creatinine concentration, and symptomatic orthostatic hypotension will be counted for each group and compared using a Poisson regression model using terms for treatment and treatment x stratum. The statistical significance of the treatment term will be used to indicate differences between CTD and placebo. If the interaction term is significant then the event rates will be reported for each stratum. The mean change from baseline in serum potassium, calcium, estimated GFR, uric acid, HgbA1C, PTH intact, and orthostatic BP will be calculated using mixed models as noted above.

Alternative study design considerations and clarifications

Choice of non-dialysis patients. Dialysis patients are challenging to study because it is more difficult to determine hypertension due to confounding by dry weight. Angioaccess makes it difficult to perform FMD. Furthermore, the number of dialysis patients—in contrast to CKD patients not on dialysis—is limited.

Timetable/Milestones

We expect to recruit and randomize a total of 160 participants in the first 3.5 years and complete the study in 4 years. This will require approximately 1 participant to be randomized per week. See table below.

Table 1: Timeline for randomization in the trial (t = 4y, n = 160)

	Year 1				Year 2				Year 3				Year 4			
Quarter	1	2	3	4	1	2	3	4	1	2	3	4	1	2	3	4
Patients	x	16	16	16	16	12	12	12	12	10	10	10	10	8	x	x

Feasibility

A feasibility assessment was performed using data from the Veterans Administration's Corporate Data Warehouse (CDW), a national repository of data compiled from the electronic medical record (EMR) system used by the Veterans Health Administration (VHA). These data include current and historical values from multiple domains such as patient medications, vitals, labs, procedures, and diagnoses, and are available from October 1st, 1999 forward. Of note, these data are updated on a daily basis and are neither filtered nor validated prior to entry into the CDW. We will use these values to screen potentially eligible participants. It is only possible to uniquely identify potential participants by accessing their EMRs using real social security numbers.

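### Safety events are judged only by significance of the treatment term, with no effect estimate or interval; if control risks are 5% to 10% (assumed), a true doubling would usually be missed at 80 per arm

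*Combined protocol and SAP*

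**What the plan says.** Under Statistical Methods, Safety analysis, subjects with each of six event types (low potassium, high calcium, gout, admission for diabetes, transient creatinine rises, symptomatic orthostatic hypotension) are counted per group. The counts are compared by a Poisson model with treatment and treatment-by-stratum terms. The decision rule is that "The statistical significance of the treatment term will be used to indicate differences"; the sentence goes on to name the arms as CTD and placebo. It is followed by: "If the interaction term is significant then the event rates will be reported for each stratum". Mean changes in laboratory values and orthostatic BP come from mixed models.

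No confidence interval, overall effect estimate, expected rate or power is given for any safety event, there or elsewhere. The only interval estimation described is for the mediated effect in the mediation analysis. Safety Assessments and Variables lists what will be monitored (weight, eGFR, CBC, clinic BP, ABPM, serious adverse events) and gives no between-group estimate.

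The Sample Size section rests on diastolic BP: the number needed "to detect a between-group difference of 5 mmHg is 68 subjects completing the study in each group". Allowing for 85% completion, this becomes 80 randomized per arm, 160 in all. Method of Randomization states: "Participants will be randomized in a 1:1 ratio".

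**The concern.** A significance test answers one question: is the observed difference larger than chance would readily produce? In a trial sized for a blood pressure difference, the answer for an uncommon event will often be no, whether or not the drug raises the risk. With significance as the only stated criterion, and no interval beside it, a reader of a non-significant result cannot tell whether a material excess has been ruled out or whether there were too few patients to see one.

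This matters more than usual here because the trial is about an adverse effect of EPO, and its introduction argues that the effect has been overlooked and underreported. The introduction also reports that in a large outcome trial "the risk of stroke was increased twofold with EPO therapy". A doubling is therefore used below as a yardstick for a material excess.

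**Working it through.** **Inputs from the documents.** 80 randomized per arm, 1:1; 68 completers per arm; "two-tailed tests and 80% power"; SD of change 10.3 mmHg; difference 5 mmHg; 85% completion (all from Sample Size and Method of Randomization).

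**Assumptions.** Two-sided alpha 0.05 (no alpha is stated); control risks of 2% to 20% (no event rates are stated); a common follow-up window for both arms and full follow-up (Safety analysis names no window).

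**Step 1: reproduce the plan's own figure.** n = 2(1.960 + 0.842)² × 10.3² / 5² = 66.6, so 67 per arm. The t distribution gives 68 (power 80.2%), and 68/0.85 = 80. The stated size reproduces with alpha 0.05, which supports that assumption. No safety event enters the calculation.

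**Step 2: power for a doubling, two-proportion test, 80 per arm.** Power = Φ{[(p2 − p1) − 1.96·SE0]/SE1}, with SE0 = √[2p̄(1 − p̄)/n] and SE1 = √{[p1(1 − p1) + p2(1 − p2)]/n}.

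- 5% to 10%: SE0 = 0.0416, SE1 = 0.0415; Φ[(0.05 − 0.0816)/0.0415] = 22.3%, so 77.7% missed. Exact enumeration of the chi-square test gives 79.1%.
- 10% to 20%: SE0 = 0.0565, SE1 = 0.0559; Φ[(0.10 − 0.1107)/0.0559] = 42.4%, so 57.6% missed. Exact enumeration gives 57.7%.

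**Step 3: the range over control risks** (two-proportion test, 80 per arm).

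| Control to treated risk | Missed |
|---|---|
| 2% to 4% | 90% |
| 5% to 10% | 79% |
| 10% to 20% | 58% |
| 15% to 30% | about 36% |
| 20% to 40% | 20% |

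**Step 4: the Poisson test** (treatment term only, two groups). The Wald approximation uses SE(log ratio) = √(1/np1 + 1/np2). For 5% to 10% this is √(1/4 + 1/8) = 0.612, and Φ(0.693/0.612 − 1.96) = 20.4%, so 79.6% missed. For 10% to 20% it is √(1/8 + 1/16) = 0.433, so 64.0% missed. Exact enumeration gives:

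| Test | 5% to 10% missed | 10% to 20% missed |
|---|---|---|
| Poisson likelihood ratio | 76.5% | 62.2% |
| Poisson Wald, model-based variance | 87.1% | 65.8% |
| Poisson Wald, robust variance | 84.2% | 60.5% |

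The plan does not say which of these would be used and does not mention a robust variance; the 62% to 87% range covers the first two rows. With a treatment-by-stratum term in the model, the treatment coefficient may refer to one UACR stratum only, depending on coding, which would lower power further.

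**Step 5: sensitivity.** With 68 per arm the pooled formula misses 80% and 63%. A one-sided 0.05 test at 80 per arm would still miss 67% and 45%. For 80% power, 435 (5% to 10%) or 199 (10% to 20%) per arm would be needed.

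**Step 6: what an interval would show.** With 8/80 against 14/80, z = 0.075/0.0545 = 1.38, not significant. The risk difference is 7.5 percentage points (95% CI −3 to +18), and the risk ratio is 1.75 (0.78 to 3.9). Even identical counts do not exclude a doubling: 8 against 8 gives a risk ratio interval of 0.39 to 2.5, and 4 against 4 gives 0.26 to 3.9.

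**The case against.** The strongest reply is that this is a minor reporting matter inside a section with a bigger fault. The rule compares CTD with placebo, but this is an open-label comparison of immediate and delayed EPO with no placebo, and the event list does not match the harms listed under Safety Assessments and Variables. That stands, and any edit must deal with it. It does not remove the present point, because correcting the arm names would leave the significance rule in place.

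Second, the size depends on assumed rates. This also stands: at a control risk of 20% the test has about 80% power for a doubling, so the difficulty concerns events at roughly 15% or below. Nothing in the documents places any listed event in the 5% to 10% band.

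Third, much is already planned. Per-group counts will exist, and a fitted Poisson model yields a rate ratio and standard error. The continuous safety measures are reasonably powered: 88% for a 0.5 SD difference at 80 per arm, 82% at 68. Serious adverse events are also monitored. All true, but a mean shift does not replace an event comparison, and nothing commits the trial to showing an interval.

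Two stronger readings are tempting and unsupported. A reader might infer that the plan will treat non-significance as evidence of safety. It does not say so; it says only what significance will indicate. A reader might also infer that EPO is expected to double the listed events. The twofold figure is for stroke, which is not on the list, and serves here only as a yardstick.

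**Conclusion.** The point holds as a defect in the stated criterion. The miss rates of 58% to 79% (two-proportion) and 62% to 87% (Poisson) rest on assumed control risks of 5% to 10%, an assumed two-sided alpha of 0.05, a common follow-up window and 80 per arm with no loss. They illustrate what the rule can detect; they do not predict this trial's events.

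The primary BP conclusion is unaffected, and limited power for events is no reason to enlarge a trial sized on BP. What changes is what the trial can say about other harms: under the written rule a non-significant term is uninformative, whereas an interval shows which excess risks remain compatible with the data. The change is worth making before analysis, since choosing how to report safety after seeing the data invites selective reporting.

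**What to change.** Replace the significance sentence in Safety analysis with:

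> For each event, the number and proportion per arm, and the overall risk difference and risk ratio with 95% confidence intervals (score or exact), will be reported whether or not the treatment or interaction test is significant. A non-significant test will not be described as no difference in harm.

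In the same edit, reconcile the reference to CTD and placebo with this trial's arms (immediate and delayed start), and reconcile the event list with the harms named under Safety Assessments and Variables.

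The cost is SAP wording and a few table columns; sample size and visits do not change. The downside is that intervals will be wide and the safety statement less favourable. The wording sets no margin, so it improves estimation and reporting but does not supply a test of safety.
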